### Serious Adverse Events

A serious adverse event is defined as any event that:

1. Results in death
2. Results in initial or prolonged inpatient hospitalization
3. Is a life-threatening experience (immediate risk of dying)
4. Results in persistent or significant disability/incapacity
5. Is a congenital abnormality/birth defect
6. Is an important medical event that may jeopardize the patient or may require medical intervention to prevent one of the outcomes listed above.

Unexpected adverse drug experiences (those not consistent with current package labeling information) will also be reported.

The causality of serious adverse events and unexpected adverse drug experiences will be assessed by the investigator(s). The IRB will be sent a report of any serious adverse event or unexpected adverse drug experience within 24 hours of the event becoming known. Reports to the DSMB will be handled in the same manner.

### **Statistical Methods**

- Sample Size

We are looking to collect sufficient data to demonstrate the efficacy and safety of TMS in bipolar depression. As this is an open label trial we will aim to treat 30 patients to achieve a reasonable sample size.

- Primary Efficacy Analysis

The primary outcome measure will be the percentage of patients who respond or remit after 30 to 35 treatments. We will subdivide patients based on the diagnosis of either bipolar I or bipolar II to compare effectiveness between those groups.

The other primary outcome will be the percentage of patients who meet criteria for onset of manic symptoms based on the YMRS. The patients will also be separated based on their diagnostic category.

- Secondary Efficacy Analysis

We will also look at the HAM-D and CGI to see the percentage of patients meeting response criteria.

For the patients meeting remission criteria, we will calculate the number of treatments required to achieve remission. Patients who only meet response criteria will be treated for 30 to 35 sessions.

Responders and remitters will also be followed for six months after the final treatment to see the durability of response. Percentage of patients' meeting relapse criteria will be calculated.

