## Aims and Hypotheses

The primary aims of this study are:

1. To provide clear open-label evidence that a standard course of TMS therapy can be effective for patients who have a diagnosis of bipolar depression and are currently on mood stabilizing medication.
2. To investigate the safety of TMS in a population at risk for activation from neuromodulation. In particular to observe if these patients are at risk for changing from a depressive state to a mixed or manic state.

Specific Hypotheses are that:

1. TMS will provide effective antidepressant treatment in patients with bipolar depression both type I and II.
2. TMS will show a shorter time to response in bipolar depressed patients compared with the available data in unipolar depressed patients.
3. TMS can be safely given in bipolar depression without inducing a manic or mixed episode switch in patients who are receiving adequate concurrent mood stabilizing medication.

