## **Background**

The current FDA approved evidence base for the treatment of bipolar depression is limited to three atypical antipsychotics, one of which is paired with an SSRI. (Nierenberg et. al. 2015). The data analyzed from the STEP-BD study supports the notion that the use of antidepressants added to mood stabilizers provides no improved outcome but may carry the risk of precipitating or supporting a mixed or manic episode. (Sachs et. al., 2007, El-Mallakh et. al. 2015) A problem in developing safe and effective treatment paradigms for bipolar depression is that the population is so heterogeneous and subgroups may require different pharmacological interventions (Altshuler et. al. 2003, Goldberg et. al. 2015)

Transcranial magnetic stimulation has had a growing impact on the treatment of major depressive disorder. There is increasing use of this modality as insurers have increasingly provided support. Sheppard Pratt has been a leader in the adoption of TMS and our clinical TMS program using the Neuronetics NeuroStar

TMS Therapy® System (See Appendix 1) has treated over 200 patients over the past six years. While there is a clear evidence base for the use of TMS in MDD, there is as yet only a small anecdotal base for its use in bipolar depression (Connolly 2012, Nola 2013, Woźniak-Kwaśniewska 2015).

We are currently doing a retrospective look at our experience in treating bipolar depression with TMS which has represented about 15% of our patient base. ([name] data in review) A preliminary evaluation of our database shows that we have treated 45 patients with bipolar depression (See Appendix 2). Four patients had their course stopped by their clinician due to side effects; none of them met the criteria for mania or mixed state. Five patients had their course completed by a different TMS provider (closer to their home) and two had incomplete data. For the 34 patients who completed a course of treatment, 26 (76.5%) met response criteria by Montgomery-Asberg Depression Rating Score (MADRS) score and 12 met remission criteria (35%). These results are numerically superior to our experience in unipolar depression where our response rate is 62% and our remission rate is 31%. In general the treatment has been well tolerated and effective. Most of these patients have a long history of either poor efficacy or safety in the use of antidepressants and inadequate antidepressant response to the use of mood stabilizers or atypical antipsychotics.

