### **Study Population**

It is estimated that up to approximately 30 patients will participate in the study at the Sheppard Pratt site with 20 additional patients enrolling at the Mayo Clinic Rochester site. Patients must have Bipolar I or Bipolar II depression as defined by the Diagnostic and Statistical Manual of Mental Disorders (DSM-5 criteria) and be taking a mood stabilizer acceptable to the principal investigator. They will not be allowed to take antidepressant medication. Their depression must be at least moderate in severity without significant symptoms of activation or mania.

Patients treated may come from the Retreat assisted living, outpatient services, outpatient practices of local psychiatrists, the Sheppard Pratt day hospital, or inpatient units. Patients enrolled at Mayo Clinic will come from their Mood program, Mood Clinic, Inpatient practice and the community. It is unlikely that current inpatients will qualify for this study as most of them will have co-morbidities, psychotic symptoms or mixed presentations which would exclude them.

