### Open Label Treatment with TMS

Stimulation will occur over the left dorsolateral prefrontal cortex at 120% magnetic field intensity relative to the subject’s resting motor threshold, at 10 pulses per second for 4 seconds, with an off time, or intertrain interval, of 26 seconds. Repositioning of the coil, per the NeuroStar User Manual, and prophylactic use of acetaminophen or ibuprofen will be allowed for subjects reporting sensations at or near the stimulation site which are uncomfortable or painful. During the first week of treatment only, in the event that the subject cannot tolerate the treatment at these dose parameters, dose intensity may be titrated downward to 110% of the motor threshold, with all other dose parameters remaining the same. Treatment sessions will last for 37.5 minutes (75 trains) to provide a total of 3,000 pulses per treatment session. All qualified study patients will receive open label TMS treatment, five times a week for a total of 30 treatments or until they meet remission criteria.

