## **Efficacy Measures and Safety Evaluations**

### Primary Efficacy Measure:

- Montgomery-Asberg Depression Rating Scale (MADRS)

Change from baseline to endpoint in MADRS total score will be the primary efficacy measure. The MADRS is a widely used rating scale for severity of mood related symptoms (Montgomery and Asberg, 1979). The scale consists of 10 items and ranges from 0 to 60. Higher scores denote more severe symptoms. The MADRS score (as opposed to the HAMD) is more sensitive to detect changes in the psychic rather than physical symptoms of depression.

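### The Sample Size text promises to demonstrate efficacy, but a single open-label arm reported as a bare percentage can only estimate a response rate

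*Combined protocol and SAP*

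**What the plan says.** The Sample Size item of Statistical Methods states the purpose: "We are looking to collect sufficient data to demonstrate the efficacy and safety of TMS in bipolar depression". It justifies the number in one clause, "we will aim to treat 30 patients to achieve a reasonable sample size". Study Population gives a larger total: about "30 patients will participate in the study at the Sheppard Pratt site with 20 additional patients enrolling at the Mayo Clinic Rochester site".

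There is no control group: "All qualified study patients will receive open label TMS treatment" (Open Label Treatment with TMS). Hypothesis 1 reads "TMS will provide effective antidepressant treatment in patients with bipolar depression both type I and II" and has no numerical criterion.

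The primary analysis is described as "The primary outcome measure will be the percentage of patients who respond or remit after 30 to 35 treatments". No interval, reference rate, success threshold, test or analysis set is attached. The efficacy section names a different primary measure, also without a test or target: "Change from baseline to endpoint in MADRS total score will be the primary efficacy measure".

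Two other places are more modest. Objectives speaks of collecting open-label data in a small population, and the first aim speaks of open-label evidence that TMS can be effective.

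Background reports the site's retrospective bipolar results (76.5% response and 35% remission among 34 who completed, of 45 treated) and presents them as numerically better than its unipolar results (62% and 31%). Neither set is adopted as a reference for the trial.

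**The concern.** To demonstrate efficacy is to show that the treatment caused the improvement. Patients enter during a depressive episode with a MADRS score of at least 20, and all of them know they are receiving active TMS. Natural course, expectation and regression to the mean therefore all sit inside the response percentage, and nothing in the design separates them from an effect of TMS.

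A second, separate gap is that the percentage has no stated precision and no stated denominator. Tying the outcome to 30 to 35 treatments can be read as leaving out patients who stop early, and the withdrawal rules allow several reasons for stopping. At stake is what may be concluded from the primary result: nothing in the plan prevents an uncontrolled percentage, possibly among completers only, from being reported as demonstrated efficacy.

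**Working it through.** **The plan's own figures.** The sample size of 30 can be neither reproduced nor contradicted, because the documents give no alpha, power, null rate, target rate, standard deviation or dropout. The retrospective figures in Background do reproduce: 45 − 4 (stopped for side effects) − 5 (finished with another provider) − 2 (incomplete data) = 34; 26/34 = 76.5%; 12/34 = 35.3%, stated as 35%.

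**Attribution.** Write the true response rate in the trial as r and the rate these patients would have shown without active TMS as b. The effect is r − b. The trial estimates r only, and the documents give no b. As an assumption, take b from 30% to 50%. With 23/30 = 76.7% observed, the implied effect runs from 76.7 − 50 = 26.7 points to 76.7 − 30 = 46.7 points. More patients narrow the interval around r but leave this 20-point spread unchanged. That is why the limit holds at any sample size.

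**Precision.** The exact (Clopper-Pearson) 95% limits for x responders among n are: lower = 0.025 quantile of Beta(x, n − x + 1); upper = 0.975 quantile of Beta(x + 1, n − x). Both totals in the documents are used, 30 and 30 + 20 = 50. The responder counts are illustrative; 23/30 and 38/50 are close to the site's 76.5%.

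| Responders | Observed | Exact 95% interval | Width (points) |
|---|---|---|---|
| 15/30 | 50.0% | 31.3–68.7% | 37.4 |
| 19/30 | 63.3% | 43.9–80.1% | 36.2 |
| 23/30 | 76.7% | 57.7–90.1% | 32.4 |
| 25/50 | 50.0% | 35.5–64.5% | 29.0 |
| 38/50 | 76.0% | 61.8–86.9% | 25.1 |

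**Denominator.** The site's own database shows how much this choice matters.

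| Rule | Response | Remission |
|---|---|---|
| Completers only | 26/34 = 76.5% (58.8–89.3%) | 12/34 = 35.3% |
| Four side-effect stops counted as failures | 26/38 = 68.4% (51.3–82.5%) | 12/38 = 31.6% |
| All 11 omitted patients counted as failures (worst case) | 26/45 = 57.8% (42.2–72.3%) | 12/45 = 26.7% |

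Counting the four side-effect stops lowers response by 76.5 − 68.4 = 8.1 points. The last row is a bound, not an estimate. If the seven patients who finished elsewhere or had incomplete data had all responded, response over all 45 would be (26 + 7)/45 = 73.3%.

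**The case against.** The strongest reply is that the protocol presents itself as small and open-label, that Objectives and the first aim claim no more than that, and that the planned outputs are descriptive. That is fair. It makes this a fault in the Sample Size text rather than in the whole protocol, and it supports aligning that text with the other two places.

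Four stronger readings are tempting, but the documents do not support them.

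- **That no result could count against Hypothesis 1.** The plan names no such value, but it also lists MADRS change as a primary measure, and no change or a worsening would count against the hypothesis. A single arm can also carry a decision rule. At one-sided alpha 0.025 and an assumed reference of 50%, at least 21/30 would be needed, with 85.4% power if the true rate is 76.5% and 51.3% if it is 68.4%. The missing rule can be supplied; the missing attribution cannot.
- **That the trial is too small because it could rarely exclude 62%.** Excluding 62% would take 25/30, with a 26% chance if the true rate is 76.5%. But Hypothesis 1 claims effectiveness, not superiority to the unipolar rate. Only Hypothesis 2 compares with unipolar patients, and it concerns time to response.
- **That the only benchmark is a completers-only figure, and that a full count puts bipolar below unipolar.** The unipolar 62% and 31% have no stated denominator, so they cannot be called completers-only. The 57.8% is a worst case.
- **That an all-treated trial result will be set against a completers-only rate.** The plan defines no analysis set and adopts no comparator.

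**Conclusion.** The point holds in a limited form. The Sample Size text claims something that a single open-label arm cannot deliver at any sample size, and the primary percentage has no interval, no reference rate and no all-treated denominator. The trial can estimate open-label response. For a result near the site's 76.5%, the exact 95% interval would be about 32 points wide with 30 patients and 25 points wide with 50.

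The attribution argument rests on the design alone. The intervals rest on illustrative responder counts and on which total applies, which the documents leave open between 30 and about 50. The assumed background rates of 30% to 50% only illustrate the argument. No conclusion is drawn about whether bipolar response is above or below the site's unipolar rate. The change is worth making because it alters what the primary result may be said to show, but it does not call for a different design.

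**What to change.** In the Sample Size item of Statistical Methods, replace the claim of demonstrating efficacy with *estimate the open-label response and remission percentages*. The hypothesis sections do not contain the claim and need no matching edit.

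In the Primary Efficacy Analysis item:

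- Report response and remission each with an exact 95% interval over all patients who start TMS.
- Count patients who stop early as non-responders. Those whose course ends because they met remission criteria count as remitters.
- Limit the conclusion on Hypothesis 1 to this estimate, and state that it is not attributed to TMS.

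Only if the Background rates are used for context, state that 76.5% and 35% come from 34 completers of 45 treated, that they become 68.4% and 31.6% if the four side-effect stops count as failures, that 57.8% and 26.7% are worst-case bounds, and that the unipolar 62% and 31% have no stated denominator.

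The cost is a few sentences, with no added patients, visits or data. The downside is a less favourable claim, and a lower reported rate if patients stop early.

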## **Objectives**

Transcranial Magnetic Stimulation (TMS) is an increasingly accepted neurostimulation- based treatment for major depressive disorder. While there is a growing anecdotal database supporting its use in bipolar depression we propose to collect open label efficacy and safety data in a small population of patients with clinically verified bipolar disorder.

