### **Study Overview and Hypotheses**

We propose to screen patients with bipolar depression I or II, who are already on acceptable mood stabilization. They may or may not be on antidepressants at the time of screening but subjects on antidepressants would be taken off them before completing the screening phase. Those patients who have a depression of at least moderate severity without significant symptoms of activation or mania will be started on a course of open label TMS treatment of up to 35 sessions. Safety and efficacy assessments will be done weekly. Patients will complete a course of treatment when they meet remission criteria (MADRS score < 10) or at the end of 30 treatments, whichever comes first. Patients who are still judged to be improving between treatment 25 and treatment 30 will be eligible to complete up to five additional treatments as the discretion of each site's principal investigator.

Patients who meet response criteria (MADRS score decreases by at least 50%) will complete the full course of 30 to 35 TMS sessions. Patients will be withdrawn for safety concerns, particularly the onset of activation suggestive of mania or a mixed state.

Patients who meet response or remission criteria will be followed monthly for up to six months to evaluate the durability of response. They will be on standard mood stabilizing medications and psychotherapy per their clinician's discretion.

The primary study hypotheses are:

1. TMS will provide effective antidepressant treatment in patients with bipolar depression both type I and II.
2. TMS will show a shorter time to response in bipolar depressed patients compared with the available data in unipolar depressed patients.
3. TMS can be safely given in bipolar depression without inducing a manic or mixed episode switch in patients who are receiving adequate concurrent mood stabilizing medication

The secondary hypothesis is:

1. The majority of treatment responders will show adequate durability of response with remitters showing better durability.

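### The planned number treated is ambiguous (30, or up to about 50 over two sites), and neither number is tied to a precision that could support a claim of demonstrated safety

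*Combined protocol and SAP*

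**What the plan says.** **Number of patients.** The Sample Size paragraph of the Statistical Methods reads: "As this is an open label trial we will aim to treat 30 patients to achieve a reasonable sample size". It names no site. The Study Population section reads: "It is estimated that up to approximately 30 patients will participate in the study at the Sheppard Pratt site with 20 additional patients enrolling"; those 20 belong to the second site. The Background and the Adverse Events section confirm that the second site is part of the study and that adverse events from both sites are reviewed together, but give no number.

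**Purpose of that number.** The Sample Size paragraph also says: "We are looking to collect sufficient data to demonstrate the efficacy and safety of TMS in bipolar depression". Other sections vary in strength. In the Objectives, "we propose to collect open label efficacy and safety data in a small population of patients with clinically verified bipolar disorder". The second aim is to "observe if these patients are at risk for changing from a depressive state to a mixed or manic state". The first aim is stronger: "To provide clear open-label evidence that a standard course of TMS therapy can be effective". The third hypothesis is that "TMS can be safely given in bipolar depression without inducing a manic or mixed episode switch" in patients on adequate mood stabilizers.

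**Planned analysis.** One primary outcome in the Statistical Methods is the percentage responding or remitting after 30 to 35 sessions. For safety: "The other primary outcome will be the percentage of patients who meet criteria for onset of manic symptoms based on the YMRS". Both are to be split by bipolar I and II. The text gives no interval, confidence level, acceptable rate or target precision for either percentage.

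**The concern.** A reader cannot tell how many treated patients the conclusions will rest on. Thirty could be the first site's share, the number treated out of a larger number enrolled, or the total for the trial.

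This matters most for safety. The observed percentages are not biased by the ambiguity, but what may be concluded from them changes. A count of zero is informative only through its upper limit, and that limit depends on the number treated. With *demonstrate* as the stated purpose and only a percentage planned, nothing in the analysis section would prevent a reported 0% from being read as support for the third hypothesis, without showing which rates remain compatible with the data.

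**Working it through.** **1. The plan's own figure.** The number 30 cannot be reproduced. No error rate, power, reference rate or interval width is given, and the only reason offered is that the size is reasonable.

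**2. Sum over sites.** Study Population: 30 + 20 = 50, as an upper estimate. Sample Size: 30 to be treated. The difference is up to 20 patients.

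**3. Can both be true?** Yes. Under Phase I: Screening, consent comes first. A patient may then fail the Phase II criteria, or be dropped because stopping an antidepressant is judged unsafe or unwanted. If 30 are treated, the loss before treatment would be:

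- 50 enrolled: 1 − 30/50 = 40% (the maximum, since 50 is a ceiling)
- 40 enrolled (illustrative assumption): 1 − 30/40 = 25%
- 30 enrolled: 0%

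The documents state no expected loss.

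**4. Precision for onset of manic symptoms.** Exact (Clopper-Pearson) two-sided 95% interval. For zero events in n, the upper limit is 1 − 0.025^(1/n):

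- n = 30: 1 − 0.025^(1/30) = 11.6%
- n = 50: 1 − 0.025^(1/50) = 7.1%

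| Events | 30 treated | 50 treated |
|---|---|---|
| 0 | 0 to 11.6% | 0 to 7.1% |
| 1 | 0.1 to 17.2% | 0.1 to 10.6% |
| 2 | 0.8 to 22.1% | 0.5 to 13.7% |

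The choice of interval does not change the picture. The one-sided 95% bound for zero events, 1 − 0.05^(1/n), is 9.5% with 30 and 5.8% with 50.

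**5. How easily zero arises.** The chance of no event is (1 − p)^n. The documents give no expected rate p for this outcome, so these values are assumptions:

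| Assumed true rate | 30 treated | 50 treated |
|---|---|---|
| 1% | 74% | 61% |
| 2% | 55% | 36% |
| 5% | 21% | 8% |

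**6. By diagnosis.** The documents do not give the split. With an assumed even split, the zero-event upper limit per group is 1 − 0.025^(1/15) = 21.8% for 30 treated, and 1 − 0.025^(1/25) = 13.7% for 50.

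**7. Precision for response.** With no response rate assumed, the widest exact interval occurs at one half: 31.3 to 68.7% at 15/30 (37.4 points), and 35.5 to 64.5% at 25/50 (28.9 points from unrounded limits).

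**The case against.** The strongest reply is that this is a small open-label study, which may choose its size pragmatically. The Objectives are modest, and the two numbers count different things: patients to be treated, and patients estimated to take part. That stands. No power calculation is needed, and a target of 30 treated fits under a ceiling of about 50 enrolled.

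Three stronger readings are tempting, and the documents do not support them:

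- *The two sections contradict each other.* They can coexist, since consent precedes screening and the Study Population figure is hedged as an estimate with an upper limit. What is missing is a sentence relating the two.
- *The plan implies a 40% loss before treatment.* That figure arises only if the full 50 enrol and exactly 30 are treated. It is a maximum.
- *The plan will declare TMS safe if no onset is seen.* No section sets such a rule, and no safety test is planned. The concern is that nothing guards against that conclusion.

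It can also be said that safety does not rest on one percentage. The study physician assesses any suggestion of mania, manic or mixed symptoms are grounds for discontinuation, patients so discontinued are followed until the symptoms resolve, and a monitoring board reviews adverse events. These measures protect patients, but they do not narrow the interval around the observed rate.

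**Conclusion.** The point holds as an ambiguity in the planned number, together with a missing statement of precision. The text supports either 30 or up to about 50 patients and does not relate them. With zero onsets, the exact two-sided 95% upper limit is 11.6% with 30 treated and 7.1% in the best case of 50 treated, so a bare 0% would not establish the third hypothesis at either size.

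The overall limits rest only on the 95% level and the exact method. The diagnosis-group limits also assume an even split, and the chances of seeing no event rest on assumed true rates.

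Two neighbouring matters are separate. The text gives no YMRS criterion for onset of manic symptoms, and that outcome is not the same event as a manic or mixed switch; the sponsor must define it. The Efficacy Measures section names change in MADRS total score as the primary efficacy measure, whereas the Statistical Methods name a percentage; that conflict must be reconciled in its own right.

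The sponsor should make the change, since it affects what may be concluded and not the observed percentages.

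**What to change.** 1. State one reconciled total in both Study Population and Sample Size, by site and as enrolled versus treated. The sponsor supplies the numbers.
2. In Sample Size, replace the promise to demonstrate efficacy and safety with: *estimate the response rate and the rate of onset of manic symptoms*. Leave the first aim as it is for now, because rewording it would prejudge the unresolved choice of primary efficacy measure.
3. Report onset of manic symptoms as a count over the number treated, and report the response or remission percentage. Give each an exact Clopper-Pearson two-sided 95% interval, overall and for bipolar I and II.
4. Add one precision sentence for the single number chosen. If 30 are to be treated, for example: *If no treated patient has onset of manic symptoms, the exact two-sided 95% upper limit is 11.6%.* If the number is 50, the figure is 7.1%.
5. Base the conclusion on the third hypothesis on that upper limit.

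**Cost.** Changes to protocol wording and to reporting; no patients or visits are added. The downside is a less favourable safety statement, with a count and an upper limit in place of demonstrated safety. The fix does not supply the YMRS onset criterion, which must be defined before the count in item 3 can be made reproducibly.
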